1.0 STUDY RATIONALE

Total knee arthroplasty (TKA) is commonly performed to improve mobility and quality of life in older adults. It is estimated that 15% of Americans age 70+ have had a TKA¹ and that ~3.5 million procedures will be performed annually by 2030.^{2, 3} Importantly, 60-80% of patients undergoing TKA have low bone mineral density (BMD).^{4, 5} Consistent with this, in our prior work low BMD was present in 119/200 (59.5%) of individuals undergoing total joint replacement at the University of Wisconsin. An important and currently underappreciated consequence of TKA is femoral bone loss, which makes the individual susceptible to periprosthetic fracture. Such fractures are not rare, occurring in up to ~5.5% of TKA patients, are challenging to repair and have devastating consequences.⁶⁻⁹ Indeed, it is reasonable to consider distal femoral periprosthetic fractures as comparable to classic osteoporosis-related hip fractures as their personal and societal consequences are strikingly similar. Specifically, periprosthetic fractures are associated with functional decline, major healthcare cost, frequent hospital readmission (> 20% within 3 months) and > 20% one year mortality.¹⁰⁻¹³ Given the aging of our population coupled with long-term survival post TKA, the numbers of older individuals with total joint replacements (and subsequent periprosthetic fractures) will increase over the foreseeable future. Specifically, in 2010, 4.3 Million people in the USA are living with TKA and each year 700,000 TKAs are performed; a number projected to triple by 2030.¹ As such, efforts to reduce periprosthetic fracture risk are essential.

TKA leads to bone loss;¹⁴⁻¹⁸ potential mechanisms for this include stress shielding, immobilization, quadriceps muscle loss and inflammatory changes following operative trauma.¹⁹⁻²¹ This decline in BMD is substantial; in our group's recent meta-analysis of 14 studies (see appended submitted manuscript), Prince, et. al., find an average distal femur BMD decline of ~16% following TKA. While absence of standard dual-energy absorptiometry (DXA) protocols and regions of interest (ROIs) compromise existing reports, these studies consistently find distal femur BMD decline to occur rapidly, mostly within 6 months, and is not restored up to 7 years later. To address the issue of DXA distal femur non-standardization, we have performed pilot work using existing DXA software and identified distal femur ROIs at which BMD can be measured with excellent precision (see appended manuscripts; Thomas, et. al., and Blaty, et. al.);^{22, 23} these regions will be utilized in this proposed study. In addition to this approach, we will also explore the clinical utility of PA and lateral knee DXA scans to evaluate bone mass change after time using existing techniques.²⁴⁻²⁶

Importantly, existing data finds that bone loss after TKA can be mitigated by pharmacologic treatment (bisphosphonates or teriparatide [TPD]).²⁷ For example, Suzuki, et. al.,²⁶ studied 17 osteoporotic women with osteoarthritis undergoing TKA and compared 12 months of TPD treatment to untreated controls. They found that the treated group had stability or a slight BMD increase while the controls experienced the expected bone loss (~9-11%). Thus, the TPD to control BMD difference after 12 months of treatment (depending on the ROI) was 8-18%. Kobayashi, et. al.,²⁸ reported a three-armed RCT comparing TPD to alendronate or placebo in patients with total hip arthroplasty; both treated groups maintained BMD while the placebo group sustained a 15% loss.

In addition to increasing periprosthetic fracture risk, inadequate bone stock is associated with subsidence around arthroplasty implants. Thus, in addition to reducing periprosthetic fracture risk, interventions to improve BMD may lead to better and more durable results after total joint arthroplasty. Consistent with this, a meta-analysis finds bisphosphonate treatment following total hip and TKA reduces revision surgery by over 50%.²⁹ To our knowledge, no similar data with bone anabolic agents exists. While beyond the scope of this proposed study, it is

plausible that bone anabolic therapy would not only reduce periprosthetic fracture risk, but also periprosthetic subsidence.

Finally, it is well accepted that falls increase fracture risk and that the age-related physical function impairment and muscle mass decline, i.e., sarcopenia, contributes to falls.³⁰⁻³² As patients may experience leg muscle loss and physical function impairment after TKA³³⁻³⁵ it is reasonable to expect this contributes to fracture risk after surgery. Consequently, we propose to collect pilot data evaluating body composition by total body DXA and bioelectric impedance spectroscopy (BIS) to evaluate change in lean mass with TKA.^{36, 37}

2.0 STUDY OBJECTIVE

Based on the above, it is clear that bone anabolic agents are of interest in orthopedic surgical patients. A recent review on non-classical use of anabolic agents concluded *“Based on a large array of literature, patients with osteoporosis require bone interventions.... Would benefit from an anabolic agent over the use of anti-resorptive agent”* and *“additional studies are needed to substantiate the role of other anabolic agents such as abaloparatide...”*³⁸ **To this end, we hypothesize that treating osteoporotic patients with ABL prior to and after TKA will significantly reduce the amount of bone loss, as measured by BMD at the 25% distal femur ROI, 15 months post TKA.** To assess the effect of ABL, we will compare the bone loss seen in this study to the 0.16 g/cm² average BMD lost in untreated osteoporotic patients at 12 and 24 months following TKA reported in Prince et.al.³⁹

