2.1 Primary Study Endpoints

Specific Aim 1: To estimate the amount of distal femur bone loss in ABL treated osteoporotic patients 15 months post TKA and to compare the bone loss to the bone loss seen in untreated osteoporotic patients 12 months following TKA as reported by the meta-analysis of Prince et.al.³⁹ The limitation of this design is the comparison to a historic control rather than a control arm in this study. The reason this design was chosen is because it would be unethical to not offer treatment to newly diagnosed osteoporotic patients. Therefore, randomization to a control arm is not possible. Furthermore, based on our recent clinical experience we believe the rate of patient choice to refuse treatment will be quite low making recruitment of a non-randomized osteoporotic control arm futile. This reflects a dramatic change in osteoporosis care within orthopedic surgical practice at UW within the past year. Lastly, it is well documented that bone loss will occur in this patient population following TKA as seen in the multiple studies summarized in the Prince article.

Specific Aim 2: To estimate the amount of distal femur bone loss in untreated osteopenic patients 15 months post TKA.

The hypothesis for this aim is that TKA will significantly reduce BMD from baseline to 15 months post surgery in osteopenic patients. To assess this we will conduct a single arm pre-post observational study.

This design was chosen because data in the literature is sparse for BMD levels pre and post TKA in an osteopenic population. Collection of these data could demonstrate significant reduction in BMD following TKA which would lead to the justification of a future prospective study comparing a bone loss mitigating treatment to no treatment (current standard of care) in osteopenic TKA patients.

Specific Aim 3: To compare the amount of bone loss in ABL treated osteoporotic patients to untreated osteopenic patients 15 months following TKA.

The hypothesis for this aim is that the percent decrease from baseline in BMD at 15 months post TKA will be greater in the untreated osteopenic group compared to the treated osteoporotic group.

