3.0 PRELIMINARY DATA

3.1 Meta-analysis of BMD loss after TKA (See Prince, et. al.)³⁹

This meta-analysis of 14 studies that quantified distal femur BMD change after primary TKA. In the distal femoral supracondylar region, mean BMD losses of 0.09 [0.05,0.13], 0.14 [0.08,0.20], 0.16 [0.10,0.23], and 0.16 [0.12,0.20] g/cm² were reported 3, 6, 12, and 24 months respectively following TKA. This corresponds to a 9.3%, 13.2%, 15.8%, and 15.4% BMD loss at these time points. In summary, there is a rapid and significant ~15% decrease in BMD in the first 6 months after TKA that is sustained to 24 months. Better understanding regarding how pre-/perioperative bone health optimization may affect BMD loss and the subsequent periprosthetic fracture risk of is essential.

3.2 Distal femoral BMD and cortical thickness after TKA compared to the contralateral (non-operated) side (See Thomas et. al, and Blaty, et. al.^{22, 23})

We initially performed measurements in 1 cm ROI increments to define BMD change throughout the femur (Thomas, et. al.). Based upon that data, we developed and evaluated a standardized technique to measure BMD and cortical thickness utilizing existing atypical femur fracture DXA software. We then compared distal femoral BMD and cortical thickness on the TKA side to the contralateral non-operative leg (Blaty, et. al.).²³ Thirty adults (15 M/15 F) age 59-80 years with well-functioning unilateral, primary TKA 2-5 years after surgery had femoral DXA scans performed. BMD and cortical thickness were measured at ROIs located at 15%, 25%, and 60% of the femur length measured from the distal notch. Femur BMD and cortical thickness were compared between limbs (TKA vs. non-operated side) by paired t-test.

BMD was 9.7%, 9.6%, and 3.2% lower ($p < 0.0001$) in the operated femur at the 15%, 25%, and 60% ROI respectively. Evaluation of this cohort by BMD status (normal, osteopenia, osteoporosis) finds distal femur BMD at the 25% ROI to be 12% lower in those with osteopenia and 10.3% lower in those with osteoporosis. Cortical width was lower by 22% ($p < 0.05$) at the 25% ROI on the TKA side but not at the 15 or 60% ROI, likely due to current software limitations. Importantly, at these distal femur ROIs, BMD reproducibility was excellent, despite

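### The Aim 1 null of -0.16 g/cm² is attributed to untreated osteoporotic patients, but the protocol does not show that source, and its closer figures are lower, so rejecting -0.16 alone does not show that ABL reduced bone loss

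*Combined protocol and SAP*

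**What the plan says.** Section 2.0 compares the loss in treated patients with 0.16 g/cm², described as the "average BMD lost in untreated osteoporotic patients at 12 and 24 months following TKA", citing the team's meta-analysis. Aim 1 in Section 2.1 repeats the attribution: the trial will "compare the bone loss to the bone loss seen in untreated osteoporotic patients 12 months following TKA". Section 8.0 tests the osteoporotic group against -0.16 g/cm² with a two-sided one-sample t-test at 5%, and reads rejection as showing that ABL is effective in keeping loss below 0.16. The endpoint is the 25% ROI of the surgical leg.

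Section 3.1 introduces the same source as follows: "This meta-analysis of 14 studies that quantified distal femur BMD change after primary TKA". It continues: "In the distal femoral supracondylar region, mean BMD losses of 0.09 [0.05,0.13], 0.14 [0.08,0.20], 0.16 [0.10,0.23], and 0.16 [0.12,0.20" (g/cm² at 3, 6, 12 and 24 months; the quotation stops inside the last bracket). The 12-month loss is also given as 15.8%. Bone status and treatment status are not described.

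Two other places bear on untreated loss in osteoporosis:
- Section 1.0, on a 12-month teriparatide study of 17 osteoporotic women having TKA: "the controls experienced the expected bone loss (~9-11" per cent).
- Section 3.2, on the pilot comparison of operated and non-operated legs at the 25% ROI: "12% lower in those with osteopenia and 10.3% lower in those with osteoporosis". Over all 30 pilot patients the difference at that ROI was 9.6%.

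Section 2.1 names the historic control as the design's limitation. It says nothing about a difference in population or region.

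**The concern.** In a single-arm test against a fixed number, that number stands in for the control group. Rejecting it says something about the drug only if it is close to what the same patients would have lost untreated, at the same site. Here the protocol gives two descriptions of where the number comes from. Section 1.0 itself says that the lack of standard ROIs weakens the existing reports, and no section relates the supracondylar region to the 25% ROI.

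If untreated loss at the 25% ROI in osteoporotic patients is less than 0.16, the null is false before ABL has any effect. The chance of a favourable result with an inactive drug then exceeds the nominal 2.5%. A conclusion that ABL reduced bone loss could rest on the choice of benchmark.

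**Working it through.** **Inputs.** Baseline 1.15 g/cm², SD 0.2, expected loss on ABL 0.02, 21 evaluable and 29 enrolled, attrition 26.5%, two-sided 5% (all Section 8.0). Pooled losses and percentages: Section 3.1. The 9-11%: Section 1.0. The 10.3%: Section 3.2.

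**1. The plan's own power.** Noncentrality = (0.16 - 0.02)/0.2 × √21 = 3.21, with df 20 and critical t 2.086. The noncentral t gives 86.2%; the plan states 86%. Enrolment: 21/(1 - 0.265) = 28.6, rounded up to 29. Both reproduce.

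**2. The percentages on the protocol's baseline.**
- 9% × 1.15 = 0.104; 10.3% × 1.15 = 0.118; 11% × 1.15 = 0.127 g/cm².
- The null itself is 0.16/1.15 = 13.9%.
- The pooled 12-month percentage gives 15.8% × 1.15 = 0.182. The baseline behind the pooled figure is about 0.16/0.158 = 1.01, not 1.15.

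**3. Chance of favourable rejection with an inactive drug.** For a true untreated loss L, this is P(T > t₀.₉₇₅), where T is noncentral t with df n - 1 and noncentrality (0.16 - L)/0.2 × √n. The nominal value is 2.5%.

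| True untreated loss L | n=21 | n=29 |
|---|---|---|
| 0.10 (lower 12-month limit, Section 3.1) | 26% | 34% |
| 0.104 (9%) | 23% | 31% |
| 0.118 (10.3%) | 15% | 19% |
| 0.127 (11%) | 11% | 14% |
| 0.16 (null true) | 2.5% | 2.5% |
| 0.182 (15.8%) | 0.7% | 0.6% |

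**4. Sensitivity to the SD.** Section 8.0 gives 0.2 as the SD of pre-surgery BMD and reuses it for change. As an assumption, take an SD of change of 0.10. With both visit SDs at 0.2, that means a pre-post correlation r with 2 × 0.2² × (1 - r) = 0.10², so r = 0.875. The n=21 probabilities for losses of 0.104, 0.118 and 0.127 become about 69%, 45% and 30%. No SD of change is given in the documents, so these show direction only.

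**5. Power against less extreme nulls.** With a true loss of 0.02, n=21 and SD 0.2, noncentrality = (L - 0.02)/0.2 × √21.

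| Null | Noncentrality | Power |
|---|---|---|
| -0.16 | 3.21 | 86% |
| -0.127 | 2.45 | 65% |
| -0.118 | 2.25 | 57% |
| -0.104 | 1.92 | 45% |
| -0.10 | 1.83 | 41% |

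**The case against.** The case for leaving -0.16 as it stands has real content.

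- **Silence is not contradiction.** Section 3.1 is a short summary, and the meta-analysis is not available here. A reader might infer that 0.16 is known to come from unselected patients and that Sections 2.0 and 2.1 misreport it. The documents do not support that: an osteoporotic subgroup cannot be excluded. What stands is that the protocol reports none.
- **Region.** A reader might infer that the benchmark was measured at a different site. Nothing maps the supracondylar region to the 25% ROI, so neither a match nor a mismatch is shown, and the size of any offset is unknown.
- **Direction.** Converting only the lower percentages is one-sided. On the same baseline, 15.8% is 0.182, and -0.16 is then the stricter null. This is fair, and the table above carries both cases.
- **Quality of the lower figures.** The 10.3% is a between-leg difference 2-5 years after surgery in a small osteoporotic part of a 30-person pilot, not a change from baseline. The 9-11% comes from a study of 17 women whose ROIs are not said to match. The pooled 24-month interval of 0.12 to 0.20 excludes 0.104 and 0.118. These figures cannot replace the null. They do show that -0.16 is not secure, and the pooled 12-month interval (0.10 to 0.23) allows a loss as low as 0.10.
- **Strictness at the stated SD.** With n=21 and SD 0.2, rejection needs an observed mean loss below 0.16 - 2.086 × 0.2/√21 = 0.069, which is less than every untreated value considered here. This is why the risk is 11-23% and not higher.
- **Disclosure.** Section 2.1 acknowledges the historic control and explains why there is no concurrent osteoporotic control. That choice is not disputed. The disclosure does not cover the population and region behind 0.16.

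**Conclusion.** The point holds, as a should-fix. Sections 2.0 and 2.1 attach 0.16 to untreated osteoporotic patients, and Section 3.1 does not bear that out. The protocol's figures closest to this population or this ROI are smaller. If they reflect the true untreated loss, a favourable result with an inactive drug has probability 11-23% at n=21 and 14-31% at n=29, instead of 2.5%. This rests on the 1.15 baseline, the SD of 0.2 used for change, and 9-11% being applicable at the 25% ROI. A smaller SD of change would raise the risk. An untreated loss of 0.182 would make the test conservative, at 0.7% for n=21.

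Two stronger readings should be resisted. One is that an inactive drug would probably be declared effective: probabilities near or above one half need an SD that the documents do not give. The other is that -0.118 should become the threshold for success: it rests on too few patients and on a comparison between legs.

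**What to change.** 1. Reconcile Sections 2.0 and 2.1 with Section 3.1. State which patients and which femoral region lie behind 0.16 g/cm², and how that region relates to the 25% ROI. Add any mismatch to the historic-control limitation in Section 2.1.
2. Keep the test against -0.16 as primary. Pre-specify that the 95% CI for mean change will be reported against nulls from -0.10 to -0.16, including -0.104, -0.118 and -0.127. If the interval lies above -0.16 but does not exclude the less extreme nulls, conclude only that the loss was smaller than the historical benchmark, not that ABL reduced it.
3. Report the Aim 3 contrast with the osteopenic group as exploratory, non-randomised support only. Section 2.1 already says that the groups differ at baseline and that the comparison may be under-powered.

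**Cost.** Text changes and one pre-specified reading of an interval that is computed anyway; no added patients or visits. The price is a stricter claim. At n=21, SD 0.2 and a true loss of 0.02, power is 86% against -0.16 but about 65%, 57% and 45% against -0.127, -0.118 and -0.104, and Section 8.0 should say so. Holding 86% against those three values would take 35, 41 and 55 evaluable patients (48, 56 and 75 enrolled at 26.5% attrition). That is not requested here.

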2.1 Primary Study Endpoints

Specific Aim 1: To estimate the amount of distal femur bone loss in ABL treated osteoporotic patients 15 months post TKA and to compare the bone loss to the bone loss seen in untreated osteoporotic patients 12 months following TKA as reported by the meta-analysis of Prince et.al.³⁹ The limitation of this design is the comparison to a historic control rather than a control arm in this study. The reason this design was chosen is because it would be unethical to not offer treatment to newly diagnosed osteoporotic patients. Therefore, randomization to a control arm is not possible. Furthermore, based on our recent clinical experience we believe the rate of patient choice to refuse treatment will be quite low making recruitment of a non-randomized osteoporotic control arm futile. This reflects a dramatic change in osteoporosis care within orthopedic surgical practice at UW within the past year. Lastly, it is well documented that bone loss will occur in this patient population following TKA as seen in the multiple studies summarized in the Prince article.

Specific Aim 2: To estimate the amount of distal femur bone loss in untreated osteopenic patients 15 months post TKA.

The hypothesis for this aim is that TKA will significantly reduce BMD from baseline to 15 months post surgery in osteopenic patients. To assess this we will conduct a single arm pre-post observational study.

This design was chosen because data in the literature is sparse for BMD levels pre and post TKA in an osteopenic population. Collection of these data could demonstrate significant reduction in BMD following TKA which would lead to the justification of a future prospective study comparing a bone loss mitigating treatment to no treatment (current standard of care) in osteopenic TKA patients.

Specific Aim 3: To compare the amount of bone loss in ABL treated osteoporotic patients to untreated osteopenic patients 15 months following TKA.

The hypothesis for this aim is that the percent decrease from baseline in BMD at 15 months post TKA will be greater in the untreated osteopenic group compared to the treated osteoporotic group.

It is understood these groups differ at baseline in BMD, but the belief is that after TKA the osteopenic group will become similar to the treated osteoporotic group. This is an exploratory analysis, and as such we may be under-powered to detect a significant effect. If trends in the differences are seen, and osteopenic patients are becoming osteoporotic after TKA, this would further bolster the need for future treatment studies in the osteopenic population.

2.2 Secondary Endpoints/Secondary aims:

- Distal femoral BMD change at the 15% and 60% ROIs
- Femur cortical thickness change at the 15%, 25% and 60% femur ROIs
- Trabecular bone score (TBS) assessment by Texture Research Investigation Platform (TRIP) software change at the 15%, 25% and 60% femur ROIs
- Patient reported outcomes; KOOS JR (knee function score), VR-12 (Veterans RAND 12 Item Health Survey) and Forgotten Joint Survey
- Precision of custom knee regions of interest
- Body composition and lean mass change
- TKA complications, e.g., revision surgery, fracture, etc

3.0 PRELIMINARY DATA

3.1 Meta-analysis of BMD loss after TKA (See Prince, et. al.)³⁹

This meta-analysis of 14 studies that quantified distal femur BMD change after primary TKA. In the distal femoral supracondylar region, mean BMD losses of 0.09 [0.05,0.13], 0.14 [0.08,0.20], 0.16 [0.10,0.23], and 0.16 [0.12,0.20] g/cm² were reported 3, 6, 12, and 24 months respectively following TKA. This corresponds to a 9.3%, 13.2%, 15.8%, and 15.4% BMD loss at these time points. In summary, there is a rapid and significant ~15% decrease in BMD in the first 6 months after TKA that is sustained to 24 months. Better understanding regarding how pre-/perioperative bone health optimization may affect BMD loss and the subsequent periprosthetic fracture risk of is essential.

3.2 Distal femoral BMD and cortical thickness after TKA compared to the contralateral (non-operated) side (See Thomas et. al, and Blaty, et. al.^{22, 23})

We initially performed measurements in 1 cm ROI increments to define BMD change throughout the femur (Thomas, et. al.). Based upon that data, we developed and evaluated a standardized technique to measure BMD and cortical thickness utilizing existing atypical femur fracture DXA software. We then compared distal femoral BMD and cortical thickness on the TKA side to the contralateral non-operative leg (Blaty, et. al.).²³ Thirty adults (15 M/15 F) age 59-80 years with well-functioning unilateral, primary TKA 2-5 years after surgery had femoral DXA scans performed. BMD and cortical thickness were measured at ROIs located at 15%, 25%, and 60% of the femur length measured from the distal notch. Femur BMD and cortical thickness were compared between limbs (TKA vs. non-operated side) by paired t-test.

BMD was 9.7%, 9.6%, and 3.2% lower ($p < 0.0001$) in the operated femur at the 15%, 25%, and 60% ROI respectively. Evaluation of this cohort by BMD status (normal, osteopenia, osteoporosis) finds distal femur BMD at the 25% ROI to be 12% lower in those with osteopenia and 10.3% lower in those with osteoporosis. Cortical width was lower by 22% ($p < 0.05$) at the 25% ROI on the TKA side but not at the 15 or 60% ROI, likely due to current software limitations. Importantly, at these distal femur ROIs, BMD reproducibility was excellent, despite

manual analysis, ranging from 0.85-1.3% at these custom sites. Based upon this work, distal femur BMD can be reproducibly measured using DXA and is ~10% lower on the TKA leg. Similarly, medial and lateral cortices are thinner at the 25% ROI. These bone changes likely increase periprosthetic fracture risk. TBS values at these ROIs are currently being obtained by colleagues at Medi-Maps (developers of TBS) using the recently released TRIP software.

